Quantifying Energetic Demands of Walking for People with Cerebral Palsy

NCT #: NCT04303078

Date: November 3, 2025

STUDY PROTOCOL

Background

Walking promotes independence, participation, fitness, and exploration in daily life. Like other activities, walking requires metabolic energy. That energy is obtained from the food we eat and the air we breathe, ultimately being used by our muscles to power movement. Experimentally, we can measure the energy being used by our muscles using indirect calorimetry, which monitors oxygen consumption and carbon dioxide generation as the body converts stored energy into the form used by muscles during activities of daily living. Decades of energetics research has demonstrated that human walking is incredibly efficient. However, for people with cerebral palsy, the energetic cost of walking is significantly increased, on average over two times higher than for typically-developing individuals. This means that for people with cerebral palsy, walking is as demanding as jogging or climbing stairs. Energetic costs of this magnitude restrict activities of daily living and causes exhaustion. While our team and many others have sought to reduce these costs through surgical interventions, rehabilitation, orthotics, or other assistive devices, these strategies have not resulted in meaningful reductions in energy. To design strategies that successfully reduce walking costs, we must first understand the underlying mechanisms contributing to elevated cost in people with cerebral palsy. This clinical trial seeks to fill this knowledge gap by examining biomechanical factors that contribute to elevated energetic costs of walking for people with cerebral palsy. Specifically, we will evaluate the energetic cost of vertical and lateral support of the body during walking for children with cerebral palsy, and compare these costs to typically-developing peers. Supporting and stabilizing the body require very little energy during unimpaired walking, accounting for less than ten percent of the total walking cost. However, the relative costs of these tasks remain unknown for people with cerebral palsy, which is problematic as they can have direct implications for treatment decisions and assistive device design. This research uses a mechatronic device to provide precise support and stabilization assistance during walking, so that we can quantify the impact of this assistance on walking cost. This research provides the foundation to create evidence-based strategies to decrease energy costs, minimize fatigue, and increase quality of life for people with cerebral palsy and other neurologic injuries.

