We will recruit children with bilateral cerebral palsy who are classified as Gross Motor Function Classification System Level II and typically-developing peers. Our sample size was designed to test the primary hypotheses that support and stabilization costs are elevated for children with cerebral palsy relative to typically-developing peers. Independent sample t-tests will be used to compare the support and stabilization costs between groups. Given the novelty of this work, we have based these estimates of our effect size on our retrospective studies and literature, where available. We estimated an effect size of 1.5 based on three comparisons. First, Unnithan et al., (2006) observed support costs in children with cerebral palsy more than two times that reported in unimpaired individuals, although the amount of assistance was not reported nor systematically controlled¹. Second, prior experiments with unilateral amputees and stroke survivors, who generally have reduced energetic costs compared to children with cerebral palsy, showed elevated support and stabilization costs. Third, the difference in fixed cost between children with cerebral palsy and typically-developing peers from our retrospective analyses supports this effect size. To detect an effect size of 1.5 with alpha equal to 0.05 and an allocation ratio of cerebral palsy to typically-developing of three to one would require 21 children with cerebral palsy and seven typically-developing peers. We used G-Power software for all estimates with power of 0.9.

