Our primary hypotheses are that support and stabilization costs are elevated in children with cerebral palsy compared to typically-developing peers. To test these hypotheses, for each participant we will calculate the walking energy in each condition. We then test the impact of vertical and lateral support using linear regression models, comparing how the walking energy changes with support. In this model, walking energy is the net dimensionless walking cost, and support assistance represents the levels of either vertical or lateral support. Secondarily, we will use linear multiple regression models to evaluate the impact of participant characteristics on support and stabilization costs. In this model, cost is the net dimensionless walking cost, assistance represents the four levels of either vertical or lateral support assistance, group represents the cerebral palsy and typically-developing cohorts, and characteristics include participant characteristics. We will evaluate whether the coefficient for group is significant, indicating the effect of support is different between groups. Participant characteristics for the regression model will include age, sex, body mass index, and minimum knee flexion during stance.

Table 1: Variable definitions

Variable	Description
Net Dimensionless Walking Cost	The energy consumed per unit time during walking, normalized for body size, calculated as the difference between walking cost and resting cost.
Support Cost:	The change in net dimensionless walking cost at maximum vertical support assistance compared to no assistance condition.
Stabilization Cost	The reduction in net dimensionless walking cost at maximum lateral stabilization assistance compared to no assistance condition.

REFERENCES

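### The secondary regression tests the group coefficient while adjusting for minimum knee flexion during stance, so that coefficient estimates only the group difference that knee posture does not explain

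*Combined protocol and SAP*

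**What the plan says.** The Statistical Analysis section separates a primary from a secondary analysis. For the primary hypotheses it states: "Independent sample t-tests will be used to compare the support and stabilization costs between groups". The sample size rests on that comparison.

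The regression is introduced as secondary and has a stated purpose: "Secondarily, we will use linear multiple regression models to evaluate the impact of participant characteristics on support and stabilization costs". Its outcome is net dimensionless walking cost. Its terms are the four assistance levels, group, and participant characteristics. The plan gives the same model a second job: "We will evaluate whether the coefficient for group is significant, indicating the effect of support is different between groups". The characteristics are then listed: "Participant characteristics for the regression model will include age, sex, body mass index, and minimum knee flexion during stance".

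The Background describes the trial as "examining biomechanical factors that contribute to elevated energetic costs of walking for people with cerebral palsy". The design section says joint kinematics come from motion capture and that the typically-developing children are matched on age and sex. Knee flexion is not a matching variable.

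The plan does not give a version of the group regression without knee flexion. It does not say which walking condition supplies the knee value, or how the adjusted group coefficient is to be interpreted.

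**The concern.** One fit serves two questions that need different covariates. Relating cost to participant characteristics is a good reason to include knee flexion. Deciding whether the groups differ is not, if knee posture is one of the ways in which cerebral palsy raises cost. Holding it equal changes the question from whether cost is higher in cerebral palsy to whether it is higher beyond what knee posture accounts for. The second question is legitimate, but it is not the conclusion that the plan attaches to the coefficient.

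What is at stake is the reading of a secondary result. With seven controls, the adjusted coefficient could be small or non-significant when the unadjusted difference is real. The plan's wording would then invite the statement that the groups do not differ, and the plan gives no rule for setting that beside the primary t-test. If the groups also differ clearly in knee flexion, collinearity widens the interval for the group term.

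**Working it through.** **Inputs from the plan (Statistical Analysis).** Effect size and alpha: "To detect an effect size of 1.5 with alpha equal to 0.05". Allocation: the plan "would require 21 children with cerebral palsy and seven typically-developing peers". Power: "We used G-Power software for all estimates with power of 0.9". Sidedness is not stated.

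**Step 1: the plan's own figure.** For an unadjusted t-test, the noncentrality is 1.5 × √(21 × 7 / 28) = 1.5 × √5.25 = 3.44 on 26 df. Two-sided power at 0.05 is 0.911, and 21 + 7 is the smallest 3:1 design that reaches 0.90. The plan's figure therefore reproduces for the unadjusted test. One-sided, 18 + 6 would suffice.

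**Step 2: what adjustment does to a group coefficient.** Let D be the group difference in knee flexion in within-group SDs, and r its within-group correlation with cost. The documents give neither, so both are assumptions. For a one-row-per-child analysis with total effect 1.5:
- expected group coefficient = 1.5 − r × D
- residual SD = √(1 − r²)
- standard-error inflation from collinearity = √(1 + D² × 5.25 / 26)
- noncentrality = coefficient × √5.25 / (residual SD × inflation), on 25 df

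Example, D = 1 and r = 0.3: the coefficient is 1.5 − 0.3 = 1.2, the residual SD 0.954, the inflation √1.202 = 1.10, and the noncentrality 1.2 × 2.291 / (0.954 × 1.096) = 2.63. Power is 0.715.

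The last column is a least-squares simulation of 8,000 runs per row that also includes three neutral covariates standing for age, sex and body mass index. Its comparator without knee flexion has power of about 0.86.

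| D | r | Coefficient | SE inflation | Power, group + knee | Power, with three more covariates |
|---|---|---|---|---|---|
| 0.5 | 0.7 | 1.15 | 1.02 | 0.93 | 0.88 |
| 1 | 0 | 1.50 | 1.10 | 0.85 | 0.79 |
| 1 | 0.3 | 1.20 | 1.10 | 0.715 | 0.635 |
| 1 | −0.3 | 1.80 | 1.10 | 0.97 | not run |
| 1.5 | 0.4 | 0.90 | 1.21 | 0.43 | not run |
| 2 | 0 | 1.50 | 1.34 | 0.69 | 0.62 |
| 2 | 0.3 | 0.90 | 1.34 | 0.34 | 0.29 |

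If D = 0 the coefficient is not attenuated. At D = 2 and r = 0.7 it falls to 1.5 − 1.4 = 0.10.

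**Step 3: how far this carries to the planned model.** The planned regression is not the model in Step 2. Its outcome is walking cost at four assistance levels, up to 28 × 4 = 112 rows with repeated measures per child. The 1.5 in the plan applies to support and stabilization costs, which Table 1 defines as changes between no and maximum assistance. No standardized effect is given for the group term of the regression. Step 2 therefore shows direction and mechanism only.

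**Step 4: which group term is exposed.**
- *One knee value per child.* The group main effect and knee flexion both vary only between children, so the group coefficient shrinks by (slope of cost on knee flexion) × (group difference in knee flexion). A group-by-assistance term, if fitted, is estimated from within-child changes. When every child completes all four levels, those changes are orthogonal to a child-level main effect. In a simulated balanced 28 × 4 dataset, adding the knee value changed that term by less than 10⁻¹³, which is rounding error.
- *A knee value from each condition.* Knee flexion now varies within a child. If assistance changes it by an amount that differs by c between the groups, and b is the slope of cost on knee flexion, the group-by-assistance term moves by b × c. It too can be attenuated.

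The plan does not say which case applies.

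**The case against.** The case against is substantial. The primary hypotheses are assigned to unadjusted t-tests, so an unadjusted group comparison is already planned and would be reported. Studying characteristics is the declared aim of the regression, and in a study of mechanisms knee flexion belongs among them. The plan never calls knee flexion a mediator. A smaller adjusted coefficient answers a different question and does not contradict the t-test.

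Most of this stands, and it limits the point to a secondary analysis. It does not remove it. The plan still reads a between-group conclusion from the adjusted coefficient, with no statement that the coefficient is conditional on knee posture.

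A reader might infer from the table that the planned regression has power of 0.34 to 0.72. The documents do not support that. The figures belong to a per-child change-score analysis with assumed D and r, and other equally admissible values leave power near or above its base (D = 0.5 with r = 0.7, or D = 1 with r = −0.3). Part of the drop from 0.911 in the last column comes from age, sex and body mass index, since the comparator with those three alone is about 0.86.

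It can also be objected that a different effect of support calls for a group-by-assistance term, which the plan does not describe, and that removing knee flexion does not supply one. That is correct, and it is a separate defect. The term that the plan says it will test is the group coefficient, and that term is exposed.

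**Conclusion.** The point holds for the secondary regression. As written, its group coefficient estimates the difference between children with cerebral palsy and typically-developing peers that knee posture does not explain, and a null result could be misread as no group difference. That knee flexion lies on the pathway is an inference from the study's aims and from its being a gait measure; the plan does not state it.

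The size cannot be derived from the documents. Attenuation needs both a group difference in knee flexion and a within-group relation to cost in the matching direction. With one knee value per child and a balanced design, only the group main effect is exposed. With condition-specific values, a group-by-assistance term can be attenuated as well.

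A reader might go further and conclude that the trial will miss its group difference, or that its sample size is undermined. Neither follows. The unadjusted t-tests and the 21 + 7 sample size stand as planned. The supported statement is that the secondary group difference can be adjusted away, not that it will be.

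**What to change.** Divide the secondary regression into two labelled models for each aim.

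1. *Group model.* Adjust for age, sex and body mass index only. Read the secondary group terms from it: group, and group by assistance if that term is fitted.
2. *Explanatory model.* Add minimum knee flexion during stance, taken from each child's no-assistance walk so that assistance cannot affect it. Describe its group coefficient as the difference not explained by knee posture.

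Report the two group coefficients side by side with confidence intervals, and state that a smaller coefficient in the second model is not evidence that the groups are alike.

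The cost is a few sentences in the analysis plan and one extra model fit per aim. No new data are needed, and the analysis of participant characteristics is kept in full.
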